3.2.2. Secondary

Safety:

- Occurrence of study vaccine-related unsolicited non-serious AEs from the time of each study vaccination through approximately 21 days after each study vaccination.
- Occurrence of all unsolicited adverse events, regardless of the assessment of seriousness or relatedness, from the time of each study vaccination through approximately 21 days after each study vaccination.
- Occurrence of MAAEs, including NOCMCs, and PIMMCs from the time of the first study vaccination through approximately 12 months after the last study vaccination.
- Occurrence of all serious adverse events (SAEs), regardless of the assessment of relatedness, from the time of the first vaccination through approximately 12 months after the last study vaccination.

Immunogenicity:

- For HAI and Neut antibodies, percentage of subjects achieving seroconversion against the influenza 2017 H7N9 vaccine strain at approximately 7, 21, and 28 days after the first study vaccination (Study Days 8, 22, 29).
- For HAI and Neut antibodies, percentage of subjects achieving titers of 1:40 or greater against the influenza 2017 H7N9 vaccine strain at baseline and approximately 7, 21, and 28 days after the first study vaccination (Study Days 8, 22, 29).
- GMTs of serum HAI and Neut antibodies against the influenza 2017 H7N9 vaccine virus at baseline and approximately 7, 21, and 28 days after the first study vaccination (Study Days 8, 22, 29).

3.2.3. Exploratory

Immunogenicity:

- For HAI and Neut antibodies, percentage of subjects achieving seroconversion and the GMTs of serum HAI antibody against the 2017 H7N9 study vaccine strain approximately 21 and 180 days after the second study vaccination (Study Days 43 and 202), stratified by age, sex, body mass index, and prior receipt of seasonal influenza vaccine(s).
- For HAI and Neut antibodies, for at least a subset of subjects, percentage achieving seroconversion, percentage with titer ≥1:40, and GMTs against antigenically drifted variants of influenza A/H7 viruses at baseline and approximately 21 and 180 days after the second study vaccination (Study Day 43 and 202).

- For HAI and Neut antibodies, percentage of subjects achieving seroconversion, percentage with titer ≥1:40, and GMTs against the 2017 H7N9 study vaccine strain at approximately 180 days after the second study vaccination (Study Day 202).
- Percentage of subjects with detectable levels of serum N9 NA specific antibody elicited by 2017 H7N9 vaccination, and the correlation of the NA content of 2017 H7N9 IIV with the elicited NA specific antibody responses at baseline and approximately 8 and 21 days after the first study vaccination (Study Day 1, 8 and 22) and 8, 21 and 180 days after the second study vaccination (Study Day, 29, 43 and 202). Note: analysis plans for this endpoint will be described in an addendum to this SAP once the NA assay has been selected.

3.3. Study Definitions and Derived Variables

For individual subjects, fold rise will be calculated as the ratio of: $\frac{post-vaccination\ titer}{pre-vaccination\ titer}$, where pre-vaccination value is always the result obtained at Day 1, prior to the priming vaccination.

HAI Seroconversion is defined as either a pre-vaccination HAI titer <10 and a post-vaccination HAI titer ≥ 40 or a pre-vaccination HAI titer ≥ 10 and a minimum four-fold rise in post-vaccination HAI titer [5].

Neut Seroconversion is defined as either a pre-vaccination Neut titer <1:10 and a post-vaccination Neut titer $\ge 1:40$ or a pre-vaccination Neut titer $\ge 1:10$ and a minimum four-fold rise in post-vaccination Neut antibody titer.

4. INVESTIGATIONAL PLAN

4.1. Overall Study Design and Plan

The protocol follows a Phase II randomized, double blind study design enrolling males and non-pregnant females aged 19 years and older who are in good health as determined by medical history and physical examination, and meet all eligibility criteria, including erythrocyte sedimentation rate (ESR), hematology, and biochemistry parameter within acceptable range, negative urine or serum pregnancy test (for females). This clinical trial is designed to assess the safety, reactogenicity, and immunogenicity of a monovalent inactivated influenza A/H7N9 virus vaccine at different dosages (3.75 mcg, 7.5 mcg, 15 mcg of HA per dose) with AS03 adjuvant, or at different dosages (15 mcg and 45 mcg of HA per dose) without adjuvant.

In this trial, subjects will be stratified by age (19-64 years or ≥65 years) then randomly assigned to 1 of 5 study groups with allocation 2:2:2:1:1 (see Table 1). The same dosage of vaccine with or without the same adjuvant will be given to subjects at both of their first and second study vaccinations. All study vaccinations will be administered IM approximately 21 days apart.

Reactogenicity will be measured by the occurrence of solicited injection site and systemic reactions from the time of each study vaccination through 7 days after each study vaccination. Unsolicited non-serious AEs will be collected from the time of each study vaccination through approximately 21 days after each study vaccination. SAEs, MAAEs, including NOCMCs, and PIMMCs, will be collected from the time of the first study vaccination through approximately 12 months after the last study vaccination. Clinical laboratory evaluations for safety will be performed on venous blood collected prior to each study vaccination and approximately 7 days after each study vaccination.

Immunogenicity testing will include performing HAI and Neut antibody assays against the 2017 A/H7N9 vaccine virus and drifted variants of the A/H7N9 virus on serum samples obtained immediately prior to each study vaccination (Days 1 and approximately Day 22), approximately 7 days after each study vaccination (Days 8 and 29), and approximately 21 and 180 days after the second study vaccination (Days 43 and 202).

Novel methods for identifying and assessing alternative correlates of protection against influenza infection are needed. To assess the NA specific antibody response to vaccination, it is first necessary to determine the NA content of inactivated influenza vaccine; this assay is under development. If successful, the NA content in a dosage specific manner can be correlated to the N9 NA-specific antibody responses elicited by the 2017 H7N9 IIV.

4.2. Discussion of Study Design, Including the Choice of Control Groups

This study uses a dose comparison concurrent control design. All subjects receive the same study product (A/H7N9 IIV) with differing dosages with or without adjuvants.

4.3. Selection of Study Population

The study population for this clinical trial is 640 males and non-pregnant females (with over-enrollment up to 720 allowed), 19 years and older, who are in good health and meet all eligibility criteria. The subjects will be recruited from the general population at the participating Vaccine Trial and Evaluation Unit (VTEU) sites that have substantial experience conducting large influenza vaccine studies.

4.4.2. Identity of Investigational Product

See the study protocol for details of study product formulation.

4.4.3. Method of Assigning Subjects to Treatment Groups (Randomization)

Enrollment/randomization will be performed through the enrollment module in the electronic data capture system maintained by the Statistical and Data Coordinating Center (SDCC).

Eligible subjects will be stratified by clinical site and age (19-64 years, ≥65 years) then randomly assigned with allocation (2:2:2:1:1) to one of 5 treatment arms indicated in Table 1. The treatment sequence was generated using permuted block randomization to provide an approximately balanced allocation to the treatment arms during the study.

4.4.4. Selection of Doses in the Study

Participants in this study are to receive two A/H7N9 vaccinations at HA doses of 3.75, 7.5, or 15 mcg with AS03 adjuvant, or at HA doses of 15 or 45 mcg without adjuvant. The 3.75, 7.5, or 15 mcg with AS03 doses are selected to evaluate safety and immunogenicity of antigen sparing dose strategies. Per FDA Guidance [5], the 15 mcg non-adjuvanted dose was selected to compare immune response with the 15 mcg adjuvanted vaccine. The 45 mcg non-adjuvanted dose is included to confirm the expected poor immunogenicity of non-adjuvanted vaccine at a high dose.

4.4.5. Selection and Timing of Dose for Each Subject

Each subject is to be randomly assigned to a study group which will define the A/H7N9 vaccine dose and receipt of adjuvant for both planned study vaccinations. The first vaccination takes place on the day of randomization, and the second vaccination takes place approximately 21 days after the first vaccination (protocol defined window of 21-28 days post first vaccination).

4.4.6. Blinding

This trial is double-blinded; subjects, investigators, study personnel performing any study-related assessments following study vaccine administration, and laboratory personnel performing antibody assays are blinded to dosage within study vaccination schedule.

The randomization scheme was generated by the SDCC and provided to unblinded study personnel (i.e., pharmacists performing study vaccination preparations and unblinded study vaccine administrators) at the participating VTEU sites who will not be not involved in study-related assessments or have subject contact for data collection following study vaccine administration.

The Data and Safety Monitoring Board (DSMB) may receive data in aggregate and presented by group. The DSMB may also be provided with expected and observed rates of the expected AEs in an unblinded fashion, and may request treatment assignment be unblinded for an individual subject if required for safety assessment. The DSMB will review grouped and unblinded data in the closed session only.

4.4.7. Prior and Concomitant Therapy

Administration of any medications, therapies, or vaccines (including prescription and over-the-counter drugs as well as herbals, vitamins, and supplements) from 60 days prior to study vaccination through 21 days post final vaccination will be solicited from the participant during screening, enrollment, and follow-up. Any reported prior therapies from up to 30 days prior to vaccination through 21 days post final vaccination will be recorded in the appropriate data collection form.

Use of concomitant medications is allowed prior to and during the trial with the exception of medications and therapies that might interfere with the evaluation of the investigational product. Medications in this category include the prohibited medication per the Subject Exclusion Criteria (protocol Section 5.1.2). In addition, the site principal investigator or appropriate sub-investigator may identify other medications that should not be used due to a risk to subject safety or assessment of reactogenicity and immunogenicity.

4.4.8. Treatment Compliance

All subjects were to receive two doses of study product administered in the clinic.

4.5. Immunogenicity and Safety Variables

See Table 2 and Table 3 for schedule of study procedures.

4.5.1. Safety Variables

Safety will be assessed by the frequency and severity of:

- 1. SAEs occurring from the time of the first study vaccination through approximately 12 months after the last study vaccination.
- 2. Solicited AEs reactogenicity events occurring from the time of each study vaccination through 7 days after each study vaccination:
 - a) Injection site reactions including pruritus, ecchymosis, erythema, induration/swelling, pain, and tenderness.
 - b) Systemic reactions including fever, feverishness, fatigue, malaise, myalgia, arthralgia, headache, and nausea.

- 3. Clinical safety laboratory AEs occurring from the time of each study vaccination through approximately 7 days after each study vaccination. Parameters to be evaluated include white blood cells (WBC), hemoglobin (Hgb), platelets (PLT), alanine aminotransferase (ALT), total bilirubin (T. Bili), and creatinine (Cr).
- 4. Unsolicited AEs non-serious AEs occurring from the time of each study vaccination through approximately 21 days after each study vaccination.
- 5. MAAEs, including NOCMCs, and PIMMCs occurring from the time of the first study vaccination through approximately 12 months after the last study vaccination.

Grading scales for injection site and systemic solicited reactions, vital signs, and clinical laboratory parameters are provided in Table 10, Table 11, Table 12, and Table 13.

4.5.2. Immunogenicity Variables

Individual HAI and Neut results will be reported by the central immunology laboratory for the homologous vaccine strain, A/Hong Kong/125/2017 (H7N9), and heterologous H7N9 strains (A/Shanghai/2/2013 and A/Guangdong/17SF003/2016). Assay results are reported as a reciprocal titer with values of $10*2^k$, where k=0, 1, 2, etc. The lower limit of detection for the HAI and Neut assays is 1:10; values below the limit of detection are imputed for analysis as one-half the limit of detection (10/2 = 5). For analysis, the geometric mean (calculated on natural log scale) of repeated results for each sample will be computed and used as the response for all subsequent calculations. The variation arising from multiple measurements for an individual at a single time point is not used in subsequent calculations. See Section 3.3 for definitions of derived variables for the analysis of HAI and Neut data.

The assay to determine the influenza virus N9 Neuraminidase (NA) antibody response to vaccination is under development. An addendum to the SAP will be generated to outline the planned analyses when assay development is complete.

All immunogenicity data will be uploaded into the SDCC's electronic data capture system.

5. SAMPLE SIZE CONSIDERATIONS

This study is planned to enroll a minimum of 160 subjects in each adjuvanted treatment arm (100 in 19-64 years age stratum, 60 in ≥65 years stratum), and 80 subjects in each unadjuvanted treatment arm (50 in 19-64 years age stratum, 30 in ≥65 years stratum). The sample size for this study was selected to obtain preliminary estimates in a time critical manner. While this study is not designed to test any specific null hypothesis, the following tables illustrate the precision and power that is available for select estimates and comparisons of interest.

Table 4 indicates the probability of observing one or more safety events, such as solicited injection site or systemic reactogenicity events or an unsolicited non-serious AE of a particular type for a single adjuvanted treatment arm/stratum (N = 60, or 100), for a single adjuvanted treatment arm combined over age strata (N=160), for all subjects receiving unadjuvanted vaccine (N = 160), and for all subjects receiving adjuvanted vaccine (N = 480).

Binomial confidence intervals (CI) are widest (have the least precision) when the response rate is 50%. Table 5 is presented to indicate the worst case scenario for precision of observed exact (Clopper-Pearson) binomial confidence intervals.

Table 6 illustrates the minimum detectable differences in the proportion of subjects responding (e.g., attaining seroconversion or a titer $\ge 1:40$) between two adjuvanted treatment arms within each stratum using a two-sided Likelihood Ratio Test and alpha = 0.05.

Over enrollment is allowed, to ensure a minimum of n=100 per adjuvanted treatment arm in the 19-64 years age stratum, therefore power calculations for this stratum assume n=100 per group. Based on previous DMID A/H7N9 trials it is expected 5% of enrolled subjects in this stratum may be excluded from analysis of the primary endpoint. In the event that only 100 subjects are actually enrolled in a treatment arm, the small dropout rates anticipated would have a minimal impact on the calculations presented in Table 7.

Within the ≥65 years treatment arm a dropout rate of up to 12% is expected based on previous DMID trials in this population, so a minimum of 60 subjects are planned to enroll in each adjuvanted treatment arm to ensure at least 50 are available for analysis of the primary immunogenicity endpoint.

Per FDA guidance [5,6], for differences in HAI antibody response rates, the lower confidence limit on the appropriate point estimate excluding equality (i.e., 0 for the difference parameter) may be sufficient to demonstrate the added value of the adjuvant. Table 8 and Table 9 show the lower bound of the 95% confidence interval for the difference in the proportion of responders between the adjuvanted and unadjuvanted arms (e.g., 15 mcg + AS03 minus 45 mcg unadjuvanted) assuming the proportion of responders in the unadjuvanted arm is 0.10 and considering a range for the proportion of responders in the adjuvanted arm ranges from 0.50 to 0.90.

6. GENERAL STATISTICAL CONSIDERATIONS

6.1. General Principles

All continuous variables will be summarized using the following descriptive statistics: n (non-missing sample size), mean, standard deviation, median, maximum and minimum. The frequency and percentages (based on the non-missing sample size) of observed levels will be reported for all categorical measures. In general, all data will be listed, sorted by site, treatment and subject, and when appropriate by visit number within subject. All summary tables will be structured with a column for each treatment arm in the following order:

- Group 1: 3.75 mcg A/H7N9 + AS03
- Group 2: 7.5 mcg A/H7N9 + AS03
- Group 3: 15 mcg A/H7N9 + AS03
- Group 4: 15 mcg A/H7N9
- Group 5: 45 mcg A/H7N9

Additional tables structured with a column for each age stratum (19-64, \geq 65) within treatment arm will be provided. All tables will be annotated with the total population size relevant to that table/treatment, including any missing observations.

6.2. Timing of Analyses

6.2.1. Expedited Interim Immunogenicity Reports

A series of Expedited Interim Immunogenicity Reports of HAI and Neut serum antibody responses comparing venous blood samples collected at baseline (D1), Visit 03 (D8), Visit 06 (D29), and Visit 07 (D43) is planned. Reports will include HAI and Neut results for approximately 25 subjects per adjuvanted treatment arm and 13 subjects per unadjuvanted treatment arm within the 19-64 year-old stratum and the first 15 subjects per adjuvanted treatment arm and 8 subjects per unadjuvanted treatment arm within the ≥65 year-old stratum. Reports will be prepared following each post-vaccination visit with analyses as described in Section 6.6.2. This information will be reviewed due to the extraordinary need to inform public health decision makers in their preparations for their response to a potential A/H7N9 pandemic. These data will be archived by the SDCC, but will not be part of the final clinical database for this study, nor will they be made available to the clinical investigators for publication.

Expedited Immunogenicity Reports will be provided by the SDCC per the study Communication Plan. Reports will include data summarized by unblinded treatment arm, but the presentation will be in a format that prevents inadvertent unblinding of any individual subject.

Tables and figures to be included in the Expedited Immunogenicity Report are indicated with the symbol † in the title.

6.2.2. Preliminary Report and CSR

Clinical, safety, and reactogenicity data through approximately 180 days after the second study vaccination will represent the primary clinical database for this trial. Once the last subject completes the visit that occurs approximately 180 days after the last study vaccination, the primary clinical database will be cleaned, monitored, and locked, and all serum samples will be sent for HAI and Neut antibody assays. Unblinded analyses of safety, reactogenicity, and available immunogenicity data (HAI and Neut antibody assays through Day 202) are planned. A preliminary report may be prepared by the SDCC after the primary clinical database is locked and all HAI and Neut data through 180 days after the last study vaccination are received. Regardless of whether a preliminary report is prepared, a "topline" set of the immunogenicity tables will be provided to DMID on an expedited timeline following laboratory database lock. These analyses may be made available to the sponsor for planning subsequent trials and to the lead principal investigator for publication. These analyses will not be used to make any decisions concerning the conduct of this trial. As it is anticipated that subjects will remain in long term safety follow-up at the time of these analyses, blinded investigators and DMID medical monitors not involved in the analysis, publication, or clinical study report preparation will be responsible for assessing SAEs and MAAEs including PIMMCs and new onset chronic medical conditions until all subjects have completed the final follow-up visit. All analyses of data included in the preliminary report for early release will be considered the final analysis of these data, and also included in the final CSR.

Tables and figures to be included in the Preliminary Report are indicated with the symbol * in the title. Topline tables to be generated after laboratory database lock are indicated with the symbol ‡ in the title.

Analysis of exploratory immunogenicity endpoints may be performed and released as the data are available from the research laboratory. Any such analyses would be considered the final analysis for the endpoint and included in the CSR.

The final CSR will be completed after the last subject's last visit is completed, and the final clinical database including all long-term safety follow-up data is cleaned, monitored and locked. Additional exploratory immunogenicity endpoint data not available at the time of CSR preparation may be included in an addendum to the CSR.

6.3. Analysis Populations

6.3.1. Safety Population

The Safety Analysis population includes all subjects who received at least one study vaccination.

6.3.2. Modified Intention-to-Treat (mITT) Population

The modified intent-to-treat (mITT) population includes all subjects who received at least one study vaccination and contributed both pre- and at least one post-study vaccination venous blood samples for immunogenicity testing (HAI or Neut antibody assays) for which valid results were reported. For analyses using the mITT population, subjects will be grouped based on randomized treatment arm.

6.3.3. Per Protocol Population

The per protocol (PP) population includes all subjects in the mITT subset with the following exclusions:

- Data from all available visits for subjects found to be ineligible at baseline due to eligibility criteria that would impact immune response.
- Data from all visits subsequent to major protocol deviations, such as:
 - o Second study vaccination not received,
 - o Second study vaccination received out of window,
 - Receipt of non-study licensed live vaccine within 30 days before or after each study vaccination,
 - Receipt of non-study licensed inactivated vaccine within 14 days before or after each study vaccination,
 - Receipt of immunosuppressive therapy (e.g., corticosteroids) within 30 days before or after each study vaccination.
- Data from any visit that occurs out of window by more than one day:
 - O Visit 3 data collected before 6 days or after 10 days post first study vaccination
 - o Visit 4 data collected before 20 days or after 29 days post first study vaccination.
 - o Visit 6 data collected before 6 days or after 10 days post second study vaccination.
 - o For subjects who did not receive the second study vaccination, visit 6 data collected before 27 days or after 31 days post first study vaccination.
 - o Visit 7 data collected before 20 days or after 29 days post second study vaccination.
 - o For subjects who did not receive the second study vaccination, visit 7 data collected before 41 days or after 50 days post first study vaccination.
 - Visit 10 data collected before 165 days or after 195 days post second study vaccination.
 - o For subjects who did not receive the second study vaccination, visit 10 data collected before 200 days or after 216 days post first study vaccination.

For analyses using the PP population, subjects will be grouped based on study vaccinations received.

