6.6 Concomitant Medications/Treatments

Administration of any medications, therapies, or vaccines will be recorded on the appropriate data collection form. Concomitant medications will include all current medications and medications taken in the 60 days prior to signing the informed consent form through approximately 21 days after the last study vaccination or early termination (if prior to 21 days after the last study vaccination), whichever occurs first. Medications reported in the electronic case report form (eCRF) are limited to those taken within 30 days prior to the first study vaccination through approximately 21 days after the last study vaccination. Prescription and over-the-counter drugs will be included as well as herbals, vitamins, and supplements. In addition, receipt of non-study influenza vaccines will be solicited through approximately 180 days after the last study vaccination, and reported in the eCRF. Use of a new medication should prompt evaluation for the occurrence of any MAAE, including a new diagnosis of chronic medical disease or condition.

Medications that might interfere with the evaluation of the investigational product(s) should not be used during the trial-reporting period (approximately 12 months after the last study vaccination) unless clinically indicated as part of the subject's health care. Medications in this category include the prohibited medications per the Subject Exclusion Criteria (see Section 5.1.2). In addition, the site principal investigator or appropriate sub-investigator may identify other medications that should not be used due to a risk to subject safety or assessment of reactogenicity and immunogenicity.

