8.2.9 Visit 10, Day 202, Safety Follow-up, Clinic Visit (Window: Day 181±14 days post second study vaccination)

- Interim medical history, including an assessment for new medical conditions, stability of chronic medical diseases, and symptoms suggestive of PIMMCs, will be obtained by interview of subjects and any changes since the previous clinic visit or contact will be noted.
- Receipt of any non-study influenza vaccines, including those that are experimental, what type (inactivated or live attenuated), what subtype (e.g., A/H3, A/H5, A/H9) and approximate date of vaccination will be recorded on the appropriate DCF, if known and not previously collected will be solicited.
- Adverse events limited to MAAEs including NOCMCs, PIMMCs, and SAEs that have occurred since the previous clinic visit or contact will be solicited
- A targeted physical examination, including an assessment for signs suggestive of PIMMCs, may be performed, if indicated based on review of interim medical history, by a study clinician licensed to make medical diagnoses and listed on the Form FDA 1572 as the site principal investigator or sub-investigator.
- Approximately 10 mL of venous blood will be collected for serum antibody assays.
- Approximately 10 mL of venous blood will be collected for future research from subjects
 who consent to collection of serum for future use, either by signing an informed consent
 form that includes collection of future use samples as a condition of study participation or
 by indicating that they opt in to sample collection for future use if the informed consent
 form allows the option to choose that option.

8.2.10 Visit 11, Day 387, Safety Follow-up, Phone Call (Window: Day 366±14 days post second study vaccination)

Subjects will be contacted by phone to query for safety events. AEs limited to MAAEs including NOCMCs, and PIMMCS, and SAEs that have occurred since the previous clinic visit or contact will be solicited. Based on the information, subjects may be asked to return to the clinic for evaluation.

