9.8. Concomitant Medications

Concomitant medications will be collected for the 30 days prior to the first study vaccination through 21 days after the second study vaccination. Concomitant medications will be coded to the Anatomical Therapeutic Classification using the WHO Drug Dictionary. The use of prior and concomitant medications taken during the study will be recorded on the CRFs. A by-subject listing of concomitant medication use will be presented (Listing 16). The use of concomitant medications during the study will be summarized by ATC1, ATC2 code, treatment arm and age stratum for the Safety population (Table 131 and Table 132).

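### The per-protocol exclusion runs to 30 days after each dose, but medications are recorded only to about 21 days after the last dose, so it cannot be fully derived for the exploratory Day 202 results

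*SAP*

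**What the plan says.** **The exclusion.** SAP 6.3.3, like Protocol 11.6.1, starts from the mITT set and removes "Data from all visits subsequent to major protocol deviations, such as" those listed. Two listed deviations carry a 30-day window: "Receipt of immunosuppressive therapy (e.g., corticosteroids) within 30 days before or after each study vaccination" and "Receipt of non-study licensed live vaccine within 30 days before or after each study vaccination". Non-study inactivated vaccines have a 14-day window.

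**The medication record.** On eCRF entries, Protocol 6.6 says that the drugs reported are "limited to those taken within 30 days prior to the first study vaccination through approximately 21 days after the last study vaccination". SAP 9.8 repeats this: "Concomitant medications will be collected for the 30 days prior to the first study vaccination through 21 days after the second study vaccination". SAP 4.4.7 gives the same end point.

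**What continues afterwards.** Protocol 6.6 makes one exception: "receipt of non-study influenza vaccines will be solicited through approximately 180 days after the last study vaccination". At Visits 08 and 09 (Protocol 8.2.7 and 8.2.8) and Visit 10 (8.2.9), the question on products received is limited to that item. Visit 10, for example, asks about "Receipt of any non-study influenza vaccines, including those that are experimental" and about their type, including live attenuated. The Appendix A footnote on concomitant medications for the follow-up period says the same.

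**Where the PP set is used at Day 202.** Titers about 180 days after dose 2 are an exploratory endpoint (Protocol 3.2.3). SAP 8.3 presents exploratory endpoints for the PP population, and the 180-day covariate summaries (8.3.1) and regression models (8.3.2) are PP only. The mITT summaries (SAP Tables 29, 31, 33 and 35) also include the 180-day time point.

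**The concern.** A prespecified exclusion needs a data source that covers its whole window. After dose 2 the rule runs to day 30 and the medication record stops at about day 21. A subject who starts a corticosteroid, or receives a non-influenza live vaccine, on day 25 should lose the Day 202 result from the PP set. Nothing in the planned data collection is sure to show it, so following the plan as written would keep in the Day 202 PP set subjects whom its own rule removes. At stake are the PP durability GMTs and seroconversion rates and the 180-day models, together with the SAP's claim that the PP set is built by the stated criteria.

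**Working it through.** No sample size, power or alpha figure is involved. The check is day arithmetic, followed by a count under a stated assumption.

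**1. Reproduce the visit days.** Dose 1 is Day 1 and dose 2 nominally Day 22. Visit 7, 21 days after dose 2, is 1 + 21 + 21 = Day 43. Visit 10, 180 days after dose 2, is 1 + 21 + 180 = Day 202. Both match the protocol.

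**2. Visit windows in days after dose 2** (the dose day counts as Day 1, so subtract 1).
- Visit 7, Day 22 + 7: 21 to 28 days.
- Visit 08, Day 61 ± 7: 53 to 67 days.
- Visit 10, Day 181 ± 14: 166 to 194 days.

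**3. Days under the 30-day rule against days recorded**, with dose 1 as day 0. The rule covers day −30 to 30 days after dose 2. The record covers day −30 to its end point.

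| Dose 2 at | Record ends after dose 2 | Rule days | Days recorded | Share | Days after dose 2 not covered |
|---|---|---|---|---|---|
| 21 | 21 | −30 to 51 = 82 | −30 to 42 = 73 | 89% | 22–30 (9 days) |
| 21 | 28 | 82 | −30 to 49 = 80 | 98% | 29–30 (2 days) |
| 28 | 21 | −30 to 58 = 89 | −30 to 49 = 80 | 90% | 22–30 (9 days) |
| 28 | 28 | 89 | −30 to 56 = 87 | 98% | 29–30 (2 days) |

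The rows ending at 28 apply if Visit 7 falls at the end of its window and every medication up to that visit is entered; Protocol 8.2.6 has all concomitant medications recorded there. The windows before dose 1, after dose 1 and before dose 2 are fully covered in every row. The 14-day inactivated-vaccine rule is also fully covered, since 14 < 21.

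**4. Which visits can be affected.** The rule removes only visits after the deviation. Anything taken before the Visit 7 sample is asked about at Visit 7, so the Day 43 PP set is not affected. The next immunogenicity sample is Visit 10, so the gap can reach only Day 202.

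**5. Which products are affected.** Live influenza vaccines are asked about to about 180 days. The gap therefore concerns immunosuppressive therapy and non-influenza live vaccines.

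**6. Size.** The documents give no rate. Assume that 5 to 15% of subjects a year start an immunosuppressant, including a systemic corticosteroid course. Expected starts = 640 × annual rate × gap days / 365.
- 9-day gap: 640 × 0.05 × 9/365 = 0.8; 640 × 0.15 × 9/365 = 2.4.
- 2-day gap: 640 × 0.05 × 2/365 = 0.2; 640 × 0.15 × 2/365 = 0.5.

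Non-influenza live vaccines are not in this count. The base of 640 is planned enrollment; subjects without a Day 202 PP result would not count.

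**The case against.** The best reply is that the mismatch is small and the plan has other sources. SAP 7.2 reviews deviations for exclusionary vaccines or medications, Protocol 16 requires deviations to be reported, Visit 10 takes an interim history, and medically attended events are collected for about 12 months. Day 202 is exploratory, and the mITT tables report it without using this rule. All of this stands and limits the consequence. It does not close the gap: a deviation is reported only if someone learns of it, and the medical history and event collection do not systematically record the drug.

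Four stronger readings are tempting, and the documents do not support them.

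- **That the rule cannot be applied, or the PP set cannot be built.** At least 89% of the rule's days are recorded. Known immunosuppression up to about 21 days after dose 2 does remove the Day 202 result.
- **That unrecorded use up to Day 202 breaks the rule.** The same assumed rates over the 159 days from Day 43 to Day 202 give 640 × 0.05 × 159/365 = 14 to 640 × 0.15 × 159/365 = 42 subjects. The rule does not cover use after day 30, so this limits how durability can be interpreted; it is not a failure of SAP 6.3.3.
- **That a 12-month ban goes unchecked.** Protocol 6.6 does say that interfering medications "should not be used during the trial-reporting period (approximately 12 months after the last study vaccination"), but it goes on to allow use that is clinically indicated in the subject's care. There is no absolute ban to verify.
- **That the age comparison of durability is biased.** The documents contain nothing on use by age, and the trial enrolls people in good health with stable conditions.

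**Conclusion.** The point holds in a narrow form. The 30-day exclusion and the roughly 21-day medication record do not match after dose 2, so for days 22 to 30 (at best, days 29 and 30 only) immunosuppressants and non-influenza live vaccines have no systematic data source. The exclusion cannot be fully derived for the exploratory Day 202 PP results.

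The likely effect is about 1 to 2 of 640 subjects over the 9-day gap. That rests wholly on the assumed 5 to 15% yearly rate and scales in proportion to it. The numerical effect on Day 202 GMTs or seroconversion is probably small, and there is no evident reason why unrecorded use should differ between the blinded, randomized arms. The case for acting is that the plan states a criterion that its own data collection cannot fully serve, and closing the gap is cheap.

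**What to change.** Align the two windows.

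- **Data collection.** At Visit 08, which falls 53 to 67 days after dose 2 and is already a phone contact, ask about immunosuppressive therapy and any licensed live vaccine, with dates, and record both through at least 30 days after the last dose. Amend Protocol 6.6, 8.2.7 and Appendix A, and SAP 4.4.7 and 9.8.
- **Analysis.** Apply the existing 30-day rule to the Day 202 data. The wording of SAP 6.3.3 need not change.
- **Optional.** Ask the same immunosuppressant question at Visits 09 and 10, so that later use, which the PP rule does not cover, can be described beside the durability results.

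The cost is one question and one eCRF field at existing contacts, with no new visit or blood draw. If those contacts have already passed, the SAP should instead state that days 22 to 30 after dose 2 are assessed from deviation reports only and that later immunosuppressant use is unknown.
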